#### **5.3.5.5 Abnormal Laboratory Values**

Not every laboratory abnormality qualifies as an adverse event. A laboratory test result must be reported as an adverse event if it meets any of the following criteria:

- Is accompanied by clinical symptoms
- Results in a change in study treatment (e.g., dosage modification, treatment interruption, or treatment discontinuation)
- Results in a medical intervention (e.g., potassium supplementation for hypokalemia) or a change in concomitant therapy
- Is clinically significant in the investigator's judgment

It is the investigator's responsibility to review all laboratory findings. Medical and scientific judgment should be exercised in deciding whether an isolated laboratory abnormality should be classified as an adverse event.

If a clinically significant laboratory abnormality is a sign of a disease or syndrome (e.g., alkaline phosphatase and bilirubin 5 × ULN associated with cholestasis), only the diagnosis (i.e., cholestasis) should be recorded on the Adverse Event eCRF.

If a clinically significant laboratory abnormality is not a sign of a disease or syndrome, the abnormality itself should be recorded on the Adverse Event eCRF, along with a descriptor indicating whether the test result is above or below the normal range (e.g., "elevated potassium," as opposed to "abnormal potassium"). If the laboratory abnormality can be characterized by a precise clinical term per standard definitions, the clinical term should be recorded as the adverse event. For example, an elevated serum potassium level of 7.0 mEq/L should be recorded as "hyperkalemia."

Observations of the same clinically significant laboratory abnormality from visit to visit should only be recorded once on the Adverse Event eCRF (see Section [5.3.5.4](#) for details on recording persistent adverse events).

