### Schedule of Assessments

	Screening Period a		Treatment Period	Treatment Discontinuation	Follow-Up Period
	Day -28 to Day -1	Day -14 to -1	Day 1 ( $\pm 3$ days) of each 3 week treatment cycle	30 ( $\pm 7$ ) days from last treatment or at initiation of other anti-cancer therapy (whichever occurs first)	
Informed Consent a	X				
Review of eligibility criteria	X				
Medical history and demographics b	X				
Age-adjusted Charlson comorbidity index	X				
12-lead ECG c	X		as clinically indicated		
Tumor sample	X (mandatory) d		Cycle 2, Day 1 (optional) e		
Weight	X		X	X	
Height	X				
Complete physical examination f	X			X	
Limited physical examination f			X g		
ECOG Performance Status	X		X g	X	
Vital signs h	X		X	X	
HIV, HBV, HCV serology i	X		as clinically indicated		
Hematology j		X	X g	X	
Coagulation (aPTT, INR)		X		X	
TSH, free T3, free T4			Every other cycle		
Serum chemistry k		X	X g	X	

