4. STATISTICAL METHODS

Categorical data will be summarized in terms of the number of patients providing data at the relevant time point, frequency counts and percentages; 95% exact Clopper-Pearson CI will also be provided when relevant. Missing data will be considered when calculating percentages. Therefore, the percentages will be based on the total number of patients in the corresponding population and not on the number of non-missing values.

Unless otherwise specified, time periods are always calculated in months. If the duration is given in days, the number of days will be divided by 365.25 and multiplied by 12 to have the period shown in months.

Continuous data will be summarized using descriptive statistics. Missing data will not be imputed, unless otherwise stated. The number of observations being included as well as the number of missing observations will be given. Further the mean, standard deviation, median, lower (25%) and upper (75%) quartile, minimum and maximum will be used to describe the data. The minimum and maximum will be reported to the same number of decimal places as the raw data recorded in the database. The mean, median, lower and upper quartiles will be reported to one more decimal place than the raw data recorded in the database, and the standard deviation to two more decimal places.

Time to event data will be estimated by the Kaplan-Meier approach with the corresponding 95% CIs.

Two-sided 95% CIs for point estimates will be calculated and presented to one more decimal places than the raw data.

All outputs (tables, listings, figures) will be produced using the statistical analysis software SAS®, version 9.3 or higher. The generated outputs will be incorporated into a Microsoft® Word 2010 document using portrait or landscape orientation, whatever is appropriate, and afterwards printed to PDF.

Mapping of unscheduled visits:

In case of an unscheduled assessment prior to the date of first study drug administration, the unscheduled assessment will be assigned to the baseline visit.

In case of an unscheduled assessment after or on the date of first study drug administration, the unscheduled assessment will be assigned to the most recent visit performed.

If a patient has more than one assessment assigned to a same visit, the latest value assigned to the visit will be used, when presenting data in summary tables by visit. In listings by patient by visit all assessments (scheduled and unscheduled) will be presented.

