4.6.1 Exposure of Study Medication

Data of atezolizumab administration will be summarized using descriptive statistics and frequency tables, respectively, based on the Safety Population, considering all exposure data until the date of last study treatment, as reported for treatment phase on the Study Completion/Early Discontinuation page of the electronic case report form (eCRF).

The duration of treatment will be calculated in units of days as the difference of the start date of treatment until the date of the most recent study treatment at data cut-off plus 1, converted into months as described in section 4.

A treatment cycle is defined as 3 weeks (+/- 3 days) in duration. An atezolizumab treatment cycle will be counted as such if the first atezolizumab administration is given for this cycle.

The relative dose intensity of atezolizumab will be calculated as the total dose administered between the first and the last administration of study treatment divided by the amount of planned dose for this period multiplied by 100.

The total dose will be calculated as the sum of all doses that were administered during the time interval between the first and the last administration of study treatment, as entered on the eCRF.

The planned dose will be calculated as the amount of drug which should have been received during the time interval between the first and the last administration of study treatment based on a dose level of 1200 mg every 3 weeks, accounting for the theoretical duration of the last cycle. Consequently, the calculation of the planned dose will be performed as follows:

$$\text{Planned dose [mg]} = \frac{(last\ dose\ date - first\ dose\ date + 21) \times 1200}{21}$$

Time on treatment will be presented in two ways. First, for the purposes of describing the exposure to atezolizumab at the time of analysis, it will be presented in standard summary form without taking account of censoring. Second, for the purposes of estimating the time spent on treatment phase by the end of the study, it will be analyzed using the Kaplan-Meier method. A patient with a recorded end of treatment phase before or on the cut-off date will be considered as having experienced an end of treatment event on the date of last dose. Patients with ongoing treatment at the cut-off date will be censored at the time of last dose before or on cut-off date.

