4.6.3 Laboratory Data

Assessments of laboratory parameters including hematology, chemistry, coagulation and thyroid panel will be performed as follows:

- For parameters with corresponding NCI-CTCAE grading, shift tables will be provided displaying baseline versus worst NCI-CTCAE grade on treatment (last date of treatment + 21 days)
- For parameters with no corresponding NCI-CTCAE grading, summary statistics will be provided for baseline values, actual values and the change from baseline values at post-baseline time points

Additionally, by-patient listings of all laboratory data, including site and patient identifier will be generated based on the safety population. A by-patient listing of ALT, AST,

alkaline phosphatase (AP) and total bilirubin assessments for potential Hy's law cases will also be provided.

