Age-adjusted Charlson comorbidity index	x				
12-lead ECG ^c	x		as clinically indicated		
Tumor sample	x ^d (mandatory)		Cycle 2, Day 1 (optional) ^e		
Weight	x		x	x	
Height	x				
Complete physical examination ^f	x			x	
Limited physical examination ^f			x ^g		
ECOG Performance Status	x		x ^g	x	
Vital signs ^h	x		x	x	
HIV, HBV, HCV serology ⁱ	x		as clinically indicated		
Hematology ^j		x	x ^g	x	
Coagulation (aPTT, INR)		x		x	
TSH, free T3, free T4			Every other cycle		
Serum chemistry ^k		x	x ^g	x	

	Screening Period ^a		Treatment Period	Treatment Discontinuation	Follow-Up Period
	Day -28 to Day -1	Day -14 to -1	Day 1 (± 3 days) of each 3 week treatment cycle	30 (± 7) days from last treatment or at initiation of other anti-cancer therapy (whichever occurs first)	
Urinalysis ^l		X	X ^g	X	
Pregnancy test ^m		X	X		
Tumor assessment ⁿ	X		Every 9 weeks ± 3 business days for 54 weeks from study treatment start; thereafter every 12 weeks ± 6 business days until confirmed PD or until study discontinuation (for patients who continue to receive atezolizumab following disease "pseudo-progression")		
EORTC QLQ-C30			Day 1 of first 3 cycles then with tumor assessments	X	
EQ-5D-5L			Day 1 of first 3 cycles then with tumor assessments	X	
Concomitant medications ^o	X		X	X	
Adverse events ^p	X		X	X	X
Study drug infusion			X		
Survival and anti-cancer therapy ^q				X	X

Abbreviations: aPTT: activated partial thromboplastin time; ECG: electrocardiogram; ECOG: Eastern Cooperative Oncology Group; EORTC: European Organisation for Research and Treatment of Cancer; INR: international normalized ratio; PD: progressive disease.

Note: Unless otherwise indicated, assessments scheduled on the study treatment days should be performed prior to initiation of study treatment infusion.

- a. Written informed consent is required for performing any study-specific tests or procedures. Results of standard-of-care tests or examinations performed prior to obtaining informed consent and within 28 days prior to study entry (except where otherwise specified) may be used for screening assessments rather than repeating such tests.
- b. Medical history includes surgical and cancer histories. Cancer history includes stage, date of diagnosis, and prior anti-cancer treatment. Reproductive status and smoking history should also be captured. Demographic information includes age, sex, and self-reported race/ethnicity.

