- p. After informed consent has been obtained, but prior to initiation of study drug, only SAEs caused by a protocol-mandated intervention should be reported. After initiation of study drug, all SAEs and AEs of special interest, regardless of relationship to study drug, will be reported until 90 days after the last dose of study drug or initiation of new anti-cancer therapy, whichever occurs first. All other AEs, regardless of relationship to study drug, will be reported until 30 days after the last dose of study drug or initiation of new anti-cancer therapy, whichever occurs first. After this period, the investigator should report any SAEs or AEs of special interest believed to be related to prior study drug treatment. The investigator should follow each AE until the event has resolved to baseline grade or better, the event is assessed as stable by the investigator, the patient is lost to follow-up, or the patient withdraws consent. Every effort should be made to follow all SAEs considered to be related to study drug or study-related procedures until a final outcome can be reported.
- q. Survival and new anti-cancer therapy follow-up information will be collected via telephone contact, patient medical records, and/or clinic visits approximately every 3 months until death, loss to follow-up, end of study, patient withdrawal or study termination by the Sponsor, whichever occurs first.

Title: MO29983 SAP 3.0 20221214 Sign-Off

Sponsor Project Number:	MO29983	PAREXEL Project Number:	231986
Sponsor Name:	F.Hoffmann-La Roche Ltd		

DocuSigned by:
[Redacted]
Signer Name: [Redacted] _____ Date _____
[Redacted] Signing Reason: I approve this document
[Redacted] Signing Time: 24-May-2023 | 9:41:50 PM CEST
[Redacted] 008B412CD24243329C5314E8576FA9C1
PAREXEL International GmbH

DocuSigned by:
[Redacted]
Signer Name: [Redacted] _____ Date _____
[Redacted] Signing Reason: I approve this document
[Redacted] Signing Time: 24-May-2023 | 6:13:01 AM CEST
[Redacted] 01A755FBBAA524180B47512D843417658
PAREXEL International GmbH

DocuSigned by:
[Redacted]
Signer Name: [Redacted] _____ Date _____
[Redacted] Signing Reason: I approve this document
[Redacted] Signing Time: 24-May-2023 | 7:47:25 PM CEST
Study Statistician _____
F.Hoffmann-La Roche Ltd
1743E9032B7349E6AE0A29043BB8CACC

DocuSigned by:
[Redacted]
Signer Name: [Redacted] _____ Date _____
[Redacted] Signing Reason: I approve this document
[Redacted] Signing Time: 24-May-2023 | 9:25:21 PM CEST

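### SAP 4.6.3 closes the worst-grade shift table 21 days after treatment, so on-schedule discontinuation-visit labs (days 23 to 37 after the last dose) of CTCAE-graded parameters reach no aggregate laboratory summary specified in the SAP

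*SAP*

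**What the plan says.** SAP 4.6.3 (Laboratory Data) splits hematology, chemistry, coagulation and thyroid parameters into two groups.

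- CTCAE-graded parameters: "shift tables will be provided displaying baseline versus worst NCI-CTCAE grade on treatment (last date of treatment + 21 days". No other aggregate display is specified for them.
- Ungraded parameters: "summary statistics will be provided for baseline values, actual values and the change from baseline values at post-baseline time points". No day limit is given.

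All laboratory data also go into by-patient listings, with a separate listing for potential Hy's law cases.

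SAP 4.6.3 does not define the last date of treatment. SAP 4.6.1 says that a patient whose treatment phase has ended "will be considered as having experienced an end of treatment event on the date of last dose".

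The Schedule of Assessments (Protocol Appendix 1, repeated in SAP Appendix 2) places the Treatment Discontinuation visit 30 (± 7) "days from last treatment or at initiation of other anti-cancer therapy (whichever occurs first"). Hematology, serum chemistry and coagulation are drawn there; the thyroid panel is not. Assessments on dosing days are done before the infusion.

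The primary objective (Protocol 2.1; SAP 2.2.5) covers changes in laboratory results both while atezolizumab is given and afterwards. Protocol 6.4 asks for frequency tables of worst grades and new Grade 3 and 4 values during treatment. It also names change from baseline in selected laboratory parameters, without a time window or a display.

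**The concern.** Because cycle labs are taken before dosing, the discontinuation visit is the main scheduled hematology and chemistry draw after the last dose. If the shift table closes before that visit can take place on schedule, a planned post-treatment safety measurement is collected and then left out of the only aggregate summary that the SAP specifies for graded parameters.

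The section is also uneven. A parameter without a CTCAE grade keeps its discontinuation-visit value in the summaries, while a graded one loses it. The 21-day limit is also shorter than other windows in the same SAP: section 4.6.2 counts treatment-emergent adverse events, and deaths on study treatment, up to 30 days after the last administration.

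At stake is the part of the primary laboratory objective that concerns the period after administration. For graded parameters it would rest on by-patient listings, and on adverse event tables for those values that qualify as adverse events.

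**Working it through.** The 21-day limit is a rule and not a derived figure, so the check is a day count. Days are counted from the last dose.

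**Inputs**
- Shift-table limit: last date of treatment + 21 days (SAP 4.6.3).
- Last date of treatment taken as the date of last dose (SAP 4.6.1). The planned-dose formula in SAP 4.6.1 likewise adds 21 days to the last dose date, to allow for the last cycle.
- Discontinuation visit: 30 ± 7 days after last treatment, or at the start of other anti-cancer therapy if earlier (Schedule of Assessments).
- Window for treatment-emergent adverse events: 30 days after last administration, or 90 days for serious events and events of special interest (SAP 4.6.2).

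**Step 1: permitted visit days.** Earliest 30 − 7 = 23; latest 30 + 7 = 37; number of days 37 − 23 + 1 = 15.

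**Step 2: overlap with the shift table.** Days from 23 to 37 that are at or before day 21: 0 of 15. The earliest visit misses by 23 − 21 = 2 days, the nominal one by 30 − 21 = 9, the latest by 37 − 21 = 16.

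**Step 3: visits brought forward.** If new anti-cancer therapy starts on day 21 or earlier, the visit moves into the window. A visit moved to day 22 is still outside.

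**Step 4: could the mapping rules bring the visit in?** SAP section 4 provides that, after the first dose, "the unscheduled assessment will be assigned to the most recent visit performed". This covers unscheduled assessments. The discontinuation visit is scheduled, so the rule does not move it.

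**Step 5: comparison with the adverse event window.** Days 23 to 30 are inside the 30-day window: 30 − 23 + 1 = 8 of 15. Days 31 to 37 are past it: 37 − 30 = 7 of 15.

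**Step 6: coverage by choice of limit**

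| Limit after last dose | Permitted visit days covered |
|---|---|
| + 21 days (SAP 4.6.3) | 0 of 15 |
| + 30 days (general adverse event window) | 8 of 15 |
| + 37 days (30 + 7) | 15 of 15 |

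Aligning the table with the 30-day adverse event window would therefore not be enough to take in the visit.

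**The case against.** **The SAP delivers what the protocol asks for.** Protocol 6.4 refers to the period during treatment, and 21 days is one dosing interval. This stands. The + 21-day table is a proper on-treatment view and should stay.

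**The objective may mean after each infusion.** From Cycle 2 on, each pre-dose draw follows the previous administration by about a cycle, so labs after administration are already in the table. This stands in part: the objective does not name the discontinuation visit. But that reading leaves no aggregate use for graded labs that the schedule requires after the last dose.

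**Protocol 6.4 leaves room for a wider summary.** It lists change from baseline in selected laboratory parameters with no window. True, but the SAP specifies no such display for graded parameters.

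**Values that matter have another route.** Protocol 5.3.5.5 states: "A laboratory test result must be reported as an adverse event if it meets any of the following criteria". The criteria are symptoms, a change in study treatment, an intervention or change in concomitant therapy, or clinical significance in the investigator's judgment. Such events enter the adverse event tables within their windows, and all values are listed. This narrows the gap considerably. What remains is mainly discontinuation-visit values that did not qualify as adverse events, plus non-serious laboratory adverse events (other than events of special interest) on days 31 to 37.

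**The date is undefined.** SAP 4.6.1 also refers to a date of last study treatment reported on the Study Completion/Early Discontinuation page. If the last date of treatment in SAP 4.6.3 were later than the last dose, the gap would shrink, and it would close if the date were 37 − 21 = 16 or more days later. The last-dose reading is the more natural one, but it remains an assumption.

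**Conclusion.** The point holds as a low-cost improvement. If the last date of treatment is the last dose, 0 of the 15 permitted days for the discontinuation visit fall inside the worst-grade shift table, unless new anti-cancer therapy brings the visit to day 21 or earlier. Graded hematology and chemistry values from that visit then appear in no aggregate laboratory summary that the SAP specifies. The number of patients whose worst grade would change cannot be derived from the documents.

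Three stronger readings are tempting, and the documents do not support them.

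- A reader might infer that post-treatment laboratory safety data are lost, or that the SAP departs from the protocol. The values are listed, those that qualify go through adverse event reporting, and the table matches the during-treatment wording of Protocol 6.4. No planned result is invalidated.
- A reader might infer that aPTT and INR have no scheduled post-baseline value in the table, since they are drawn only at screening and at discontinuation. That holds only if they are analysed as graded, which the documents do not say. If they are ungraded, they are summarised without a day limit.
- A reader might infer that one-dose patients drop out of the table. A Cycle 2 pre-dose draw, if taken, may fall between day 21 − 3 − 4 = 14 and day 21 + 3 = 24. Of these 11 days, 8 (days 14 to 21) are inside the window.

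**What to change.** In SAP 4.6.3:

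1. Keep the + 21-day shift table as the on-treatment view, and state that the last date of treatment is the date of last dose.
2. Add one worst-grade shift table that also includes the Treatment Discontinuation visit labs. It should run to last dose + 37 days, or to the start of new anti-cancer therapy if earlier, with labs on that start date included.
3. Label the second table as added after sign-off, since the SAP already carries a page titled "MO29983 SAP 3.0 20221214 Sign-Off".

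The cost is two or three sentences in a SAP addendum and one more set of shift tables on data already collected. The + 21-day table does not change if last dose is the intended reading.

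There are downsides to state with the table. Some late values may reflect disease progression. Days 31 to 37 run past the window for non-serious treatment-emergent events. Worst-grade percentages may look slightly less favourable than in the on-treatment table. Discontinuation labs drawn after day 37 would still be in listings only.

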### **9.5 ADMINISTRATIVE STRUCTURE**

This trial will be sponsored and managed by F. Hoffmann-La Roche Ltd. and was designed in collaboration with outside guidance from a Steering Committee. The Sponsor will provide clinical operations management, data management, and medical monitoring. An iDMC will review SAEs and accumulating safety data.

Approximately 200 sites in approximately 30 countries across Europe, North America, Latin America, North Africa, the Asia Pacific region, and the Middle East will participate to enroll approximately 1000 patients.

Enrollment will occur through an IxRS system. Central facilities will be used for certain study assessments throughout the study (e.g., specified laboratory tests and biomarker analyses) as specified in Section 4.5. Accredited local laboratories will be used for routine monitoring; local laboratory ranges will be collected.

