**Table 4 Management Guidelines for Endocrine Events**

Event	Management
Asymptomatic hypothyroidism	
 
Continue atezolizumab.
 
Initiate treatment with thyroid replacement hormone.
 
Monitor TSH closely.
 

Symptomatic hypothyroidism	
 
Withhold atezolizumab.
 
Initiate treatment with thyroid replacement hormone.
 
Monitor TSH closely.
 
Consider patient referral to endocrinologist.
 
Resume atezolizumab when symptoms are controlled and thyroid function is improving.
 

Asymptomatic hyperthyroidism	
TSH <math>\geq 0.1</math> mU/L and <math>< 0.5</math> mU/L:
 
 
Continue atezolizumab.
 
Monitor TSH every 4 weeks.
 
Consider patient referral to endocrinologist
 
 
TSH <math>< 0.1</math> mU/L:
 
 
Follow guidelines for symptomatic hyperthyroidism.
 
Consider patient referral to endocrinologist
 

Symptomatic hyperthyroidism	
 
Withhold atezolizumab.
 
Initiate treatment with anti-thyroid drug such as methimazole or carbimazole as needed.
 
Consider patient referral to endocrinologist.
 
Resume atezolizumab when symptoms are controlled and thyroid function is improving.
 
Permanently discontinue atezolizumab and contact Medical Monitor for life-threatening immune-mediated hyperthyroidism.c
 

MRI=magnetic resonance imaging; TSH=thyroid-stimulating hormone.

a Atezolizumab may be withheld for a longer period of time (i.e.,  $> 12$  weeks after event onset) to allow for corticosteroids (if initiated) to be reduced to the equivalent of  $\leq 10$  mg/day oral prednisone. The acceptable length of the extended period of time must be based on an assessment of benefit–risk by the investigator and in alignment with the protocol requirements for the duration of treatment and documented by the investigator. The Medical Monitor is available to advise as needed.

b If corticosteroids have been initiated, they must be tapered over  $\geq 1$  month to the equivalent of  $\leq 10$  mg/day oral prednisone before atezolizumab can be resumed.

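### SAP 4.6.3 plans no count of patients moving outside the reference range on laboratory tests without a CTCAE grade, and does not say whether the thyroid tests are among them

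*SAP*

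**What the plan says.** SAP 4.6.3 opens with one list of panels: "Assessments of laboratory parameters including hematology, chemistry, coagulation and thyroid panel will be performed as follows". Two rules follow.

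- For tests that have a CTCAE grade, "shift tables will be provided displaying baseline versus worst NCI-CTCAE grade on treatment", with the on-treatment window ending 21 days after the last treatment date.
- For the others: "For parameters with no corresponding NCI-CTCAE grading, summary statistics will be provided for baseline values, actual values and the change from baseline values". These are given separately for each visit after baseline.

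The section does not assign any panel to either rule. SAP section 4 defines the summary statistics: besides the number of observations and the number missing, "Further the mean, standard deviation, median, lower (25%) and upper (75%) quartile, minimum and maximum will be used to describe the data". SAP 4.6.3 adds that "by-patient listings of all laboratory data, including site and patient identifier will be generated based on the safety population".

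Protocol 6.4 plans frequency tables of worst laboratory grades and of new Grade 3 and 4 values, which again need a grade. Protocol 9.5 says that local laboratories do routine monitoring and that "local laboratory ranges will be collected". Protocol Appendix 1 schedules TSH, free T3 and free T4 at every other treatment cycle and shows no screening entry for them.

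**The concern.** Change in laboratory results is part of the primary objective (Protocol 2.1, SAP 2.2.5). A safety reader asks of each test how many patients became abnormal, and in which direction. For a graded test the shift table answers in terms of grade. For an ungraded test no planned table answers, because each statistic describes the pooled distribution at one time point and nothing takes each patient's most extreme value across visits.

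The thyroid tests are where this matters most. Hypothyroidism and hyperthyroidism are both events of special interest, and they move TSH in opposite directions. Raw values from about 200 sites' local laboratories would be pooled without the ranges that were collected to interpret them. If TSH falls under the ungraded rule, the number of patients with new high or low values could be had only by counting through the listings.

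**Working it through.** **Figure stated in the plan.** The only design figure is the Clopper-Pearson table in SAP 2.3. All nine rows reproduce at N = 1000; for 5 events the limits are 0.163% and 1.163%, against the stated 0.16% and 1.16%. No figure is given for laboratory data, and this point does not depend on the table.

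**Which abnormal thyroid values reach an adverse event table.**

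1. SAP 4.6.2 makes hypothyroidism and hyperthyroidism events of special interest, tabulates these events by category, preferred term and worst grade, and adds a by-patient listing of immune-related thyroid disorders. All of this starts from a reported event.
2. Protocol 5.3.5.5 requires a laboratory result to be reported if it comes with symptoms, changes study treatment, leads to an intervention or changed concomitant therapy, or is judged clinically significant.
3. Under Protocol Appendix 11 Table 4, asymptomatic hypothyroidism leads to hormone replacement, and TSH below 0.1 mU/L follows the symptomatic guideline, which withholds atezolizumab. Both actions meet step 2.
4. For "Asymptomatic hyperthyroidism" with TSH from 0.1 to below 0.5 mU/L, the same table continues treatment, monitors TSH and suggests considering referral. Such a patient need not meet any trigger in step 2 other than the investigator's judgment.

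A value of the kind in step 4, if not judged significant, appears only in the laboratory listing and possibly as a minimum or maximum.

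**What the planned statistics show.** This illustration uses assumed TSH values, none from the documents: 1,000 patients, one simulated draw per row.

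- Baseline: b = exp(Normal(ln 1.8, 0.5)).
- Unaffected patients: v = b × exp(Normal(0, 0.25)).
- Shifted high: v = exp(Normal(ln h, 0.5)), with h = 8 or 20.
- Shifted low: v uniform on 0.01 to 0.09.
- Change: c = v − b, in mU/L.

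| High / low | h | Mean c | SD c | Median c | Q1 c | Q3 c | Min v | Max v |
|---|---|---|---|---|---|---|---|---|
| 0% / 0% | draw 1 | 0.09 | 0.62 | −0.01 | −0.25 | 0.32 | 0.21 | 13.57 |
| 0% / 0% | draw 2 | 0.04 | 0.62 | −0.03 | −0.29 | 0.28 | 0.39 | 8.76 |
| 5% / 5% | 8 | 0.30 | 1.97 | 0.03 | −0.30 | 0.40 | 0.01 | 25.87 |
| 5% / 5% | 20 | 1.04 | 5.47 | −0.01 | −0.33 | 0.35 | 0.01 | 60.31 |
| 10% / 3% | 8 | 0.73 | 2.86 | 0.02 | −0.31 | 0.47 | 0.01 | 29.50 |
| 10% / 3% | 20 | 2.38 | 8.58 | 0.03 | −0.25 | 0.48 | 0.01 | 100.96 |
| 3% / 10% | 8 | 0.08 | 2.00 | −0.06 | −0.41 | 0.28 | 0.01 | 23.88 |
| 3% / 10% | 20 | 0.55 | 4.95 | 0.00 | −0.36 | 0.33 | 0.01 | 76.53 |
| 10% / 10% | 8 | 0.59 | 2.76 | 0.01 | −0.33 | 0.42 | 0.01 | 24.88 |
| 10% / 10% | 20 | 2.12 | 8.22 | −0.01 | −0.34 | 0.41 | 0.01 | 93.95 |

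- The median change stays within ±0.06 throughout. With shifts, Q1 runs from −0.41 to −0.25 and Q3 from 0.28 to 0.48; without shifts, −0.29 to −0.25 and 0.28 to 0.32.
- The mean nearly cancels in one mix only (3% / 10%, h = 8: 0.08). Elsewhere it rises, because falls are bounded at zero and rises are not.
- SD, minimum and maximum clearly register that something happened, but they do not count. Compare 10% / 3% with 10% / 10% at h = 8, that is 30 against 100 low patients: median 0.02 and 0.01, Q1 −0.31 and −0.33, mean 0.73 and 0.59, SD 2.86 and 2.76, minimum 0.01 in both. These are separate draws, so small differences are partly noise.

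**The case against.** The strongest reply is that thyroid safety is already well covered. Baseline and actual values are summarised as well as change, with SD, minimum and maximum. All laboratory data are listed. Thyroid disorders have event tables that give counts and direction, plus their own listing. Most thyroid abnormalities that are acted on become reportable events. The study is descriptive and tests no hypothesis, so one more table is a matter of presentation. All of this stands, and it keeps the point small.

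A reader might infer something stronger: that the ungraded tests are shown only as change from baseline, that opposite shifts cancel, and that thyroid dysfunction is therefore hidden. The documents do not support that. SAP 4.6.3 also summarises baseline and actual values, cancellation does not occur in SD, minimum or maximum and only rarely in the mean, and the event tables show reported disorders.

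A reader might also infer that the documents place the thyroid panel under the ungraded rule. They do not. Appendix 11 Table 4 handles thyroid results by TSH level and symptoms, which suggests it, but a management scheme does not settle whether a CTCAE grade exists. The same appendix, in its footnotes on cytokine-release syndrome, separates management grading from the CTCAE grade used for reporting.

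What the reply does not supply is a table that counts new low or high values on an ungraded test.

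**Conclusion.** The point holds as a minor gap in the planned displays. For any laboratory test without a CTCAE grade, no planned laboratory table gives the number of patients with new abnormal values or their direction, although the ranges needed are collected. SAP 4.6.3 also leaves open which rule covers TSH, free T3 and free T4.

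For the thyroid tests the affected patients are those with abnormal values that trigger no adverse event report. The documents give no basis for estimating how many there are. The size shown is therefore only the insensitivity of the centre of the distribution, and it rests on the assumed TSH distribution and shift rates. If the sponsor intends a CTCAE grade for these tests, the thyroid example falls away, but the gap remains for every other ungraded test.

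**What to change.** In SAP 4.6.3:

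1. State for TSH, free T3 and free T4 whether the graded or the ungraded rule applies.
2. For ungraded tests, add shift tables of low, normal and high by local reference range: baseline against the lowest, and baseline against the highest, on-treatment value. Use the window already set for graded tests.
3. Include a row for missing baseline. The schedule has no screening thyroid test, and sampling at every other cycle does not clearly guarantee a sample before the first dose. SAP section 4 bases percentages on the whole population, so missing values need to be visible.
4. Keep the planned summary statistics.
5. Optionally, count patients in the two TSH bands of Appendix 11 Table 4 (0.1 to below 0.5, and below 0.1 mU/L). This serves low TSH only, because that table has no band for high TSH.

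This changes the display only and touches no clinical rule. It needs no new data and costs one or two extra table shells.
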